4. ELIGIBILITY CRITERIA

4.1. Inclusion criteria

- 1) Should be at least 18 years of age,
- 2) Male or female, female should have negative pregnancy test,
- 3) Diagnosed with COVID-19 and confirmed SARS-CoV-2 viral infection, prior positive viral results allowed,
- 4) Informed consent form signed by patient or by a legally authorized representative,
- 5) Hospitalized and requiring oxygen support, NIAID 8-point ordinal score 2, 3, 4, regardless of ARDS (Appendix A), intubation for invasive mechanical ventilation should be within 7 days,
- 6) Women of childbearing potential, under the age of 54 years, who use adequate contraception and who agree to use adequate contraception for the duration of the study.

4.2. Exclusion criteria:

- 1) Patients who are pregnant, breastfeeding, or have a positive pregnancy test result before enrollment,
- 2) Patients previously enrolled in the CD24Fc study,
- 3) Intubation for invasive mechanical ventilation is over 7 days,
- 4) Documented acute renal or hepatic failure,
- 5) The investigator believes that participating in the trial is not in the best interests of the patient, or the investigator considers unsuitable for enrollment (such as unpredictable risks or subject compliance issues).

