8.1.2. Definition of Serious Adverse Events (SAE) in COVID-19

An adverse event (AE) or suspected adverse reaction is considered "serious" if, in the view of either the investigator or sponsor in this COVID-19 clinical trial, it results in any of the following outcomes: death, or a life-threatening adverse event other than COVID-19 progression that requires admission to the ICU, or organ failures in addition to COVID-19 respiratory failure.

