8.3. Serious Adverse Event Reporting

The study clinician will immediately report to the sponsor any serious adverse event, whether or not considered study intervention related, including those listed in the protocol or investigator brochure and must include an assessment of whether there is a reasonable possibility that the study intervention caused the event. Study endpoints that are serious adverse events (e.g., all-cause mortality) must be reported in accordance with the protocol unless there is evidence suggesting a causal relationship between the study intervention and the event (e.g., death from anaphylaxis). In that case, the investigator must immediately report the event to the sponsor.

All Grade V event (death) should be reported as SAE to CRO and sponsor in a timely manner.

All serious adverse events (SAEs) will be followed until satisfactory resolution or until the site investigator deems the event to be chronic or the participant is stable. Other supporting

documentation of the event may be requested by the study sponsor and should be provided as soon as possible.

The study sponsor will be responsible for notifying the Food and Drug Administration (FDA) of any unexpected fatal or life-threatening suspected adverse reaction as soon as possible, but in no case later than 7 calendar days after the sponsor's initial receipt of the information. In addition, the sponsor must notify the FDA and all participating investigators in an Investigational New Drug (IND) safety report of potential serious risks, from clinical trials or any other source, as soon as possible, but in no case later than 15 calendar days after the sponsor determines that the information qualifies for reporting.

The Medical Monitor will advise the Sponsor regarding the safety of the study participants as well as the continuing safety and scientific validity of the trial. The Medical Monitor may also review the results of any planned analysis, if applicable. If the data analysis shows significant findings with regards to safety, the Medical Monitor may recommend modification of the protocol, Informed Consent, and/or monitoring of the study. In these cases, the regulatory authorities and local review committees may be notified. The Medical Monitor may also stop the study for reasons of safety.

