10.5. Interim Analysis and Stopping Rules

This study will establish an independent Data and Safety Monitoring Board (DSMB) for interim analysis. The composition, task responsibilities and implementation details of DSMB will be specified in the DSMB charter.

Two blinded safety reviews will be performed, respectively, when 50% and 75% of the planned enrollment has occurred with follow-up time reaching D15 and mortality data are available.

The study will also include an interim analysis at 70% of the required 146 events. The final analysis will be carried out after all 270 subjects have been randomized, dosed and completed the study.

In the interim analysis, the DSMB will re-estimate the sample size to determine whether it supports increasing the number of clinical improvement event targets. Chen's method will be used to re-estimate the sample size (37).

Safety reviews and stopping rules

The study have two blinded safety reviews respectively, when 50% and 75% of the planned enrollment has occurred with follow-up time reaching Day 15 and SAE data are available. DSMB will be provided with list of SAE including mortality and may unblind the data at its discretion to evaluate the balance of SAE in the two study arms.

Stopping rules

If the DSMB found that SAE is significantly higher in the CD24Fc arm, it may recommend termination of the trial after review of potential benefit of the study drug by unblinding all study subjects. Sponsor will make final decision based on the recommendation of DSMB.

Sample Size Re-Estimation

The interim analysis for the primary endpoint only will be performed after reaching 146 events (70% of information). A sample size reassessment of efficacy will be performed.

There sample size re-estimation 146 events will be based on preliminary data that are not 100% source-verified. The method will be based on Chen et al as stated in the protocol. If the conditional power is < 50% or >85%, the trial will continue without a sample size increase; whereas if the conditional power is between 50% to 85%, the sample size will be re-calculated to

have 85%. To maintain trial integrity, the DSMB will pick a sample size in a nearest interval with 5 patients. For example, if the re-estimated sample size is 287, the DSMB could pick any number in the interval of 285 to 289. Also, the maximum increased sample size will not be more than 70 patients above what is needed to observe 208 events.

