13. APPENDIX A

NIAID 8-point Ordinal Scale for COVID-19 (NCT04280705)

The ordinal scale is an assessment of the clinical status at the first assessment of a given study day. The scale is as follows:

- 1) Death;
- 2) Hospitalized, on invasive mechanical ventilation or extracorporeal membrane oxygenation (ECMO);
- 3) Hospitalized, on non-invasive ventilation or high flow oxygen devices;
- 4) Hospitalized, requiring supplemental oxygen;
- 5) Hospitalized, not requiring supplemental oxygen - requiring ongoing medical care (COVID-19 related or otherwise);
- 6) Hospitalized, not requiring supplemental oxygen – no longer requires ongoing medical care;
- 7) Not hospitalized, limitation on activities and/or requiring home oxygen;
- 8) Not hospitalized, no limitations on activities.

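### On its natural reading, the ICU-admission condition in the serious adverse event definition leaves survived life-threatening events in patients already in ICU off the DSMB's list and out of the stopping rule

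*Combined protocol and SAP*

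**What the plan says.** Section 8.1.2 replaces the usual seriousness criteria with a closed list of three outcomes: death, "a life-threatening adverse event other than COVID-19 progression that requires admission to the ICU", "or organ failures in addition to COVID-19 respiratory failure". Whether one of them has occurred is decided "in the view of either the investigator or sponsor in this COVID-19 clinical trial".

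Section 4.1 admits patients with "NIAID 8-point ordinal score 2, 3, 4, regardless of ARDS". Appendix A defines score 2 as invasive mechanical ventilation or ECMO. Section 11.1.3, on surrogate consent, describes ventilated participants as being in ICU.

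The safety reviews in 10.5 give the DSMB a list of SAEs, deaths included, once 50% and 75% of planned enrollment have reached Day 15. The stopping rule there begins "If the DSMB found that SAE is significantly higher in the CD24Fc arm" and lets the board recommend termination after weighing benefit. The synopsis says the same. Neither place sets a numerical threshold.

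Under 8.3, sites report SAEs to the sponsor immediately, and the sponsor must notify the FDA of "any unexpected fatal or life-threatening suspected adverse reaction as soon as possible", with an outer limit of 7 calendar days from its own first receipt of the information. Under 8.1.6 and 8.2, Grade III to V events that are not SAEs are recorded and passed to the sponsor in timely fashion, with no fixed deadline.

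**The concern.** The life-threatening limb is tied to a change of location, and some of the eligible population has already made that change at baseline. Others make it later, when they deteriorate and are transferred. Once in ICU, a patient who has a life-threatening arrhythmia, bleed or infusion reaction and survives it without another organ failing has met none of the three listed outcomes. The same event in a ward patient who is then transferred is an SAE.

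This matters because SAE imbalance is what the stopping rule acts on, and the SAE list is what the safety reviews are specified to receive. These events are also relevant to this drug. Section 8.5 asks for monitoring of severe infusion reactions, with hypotension and hypoxemia as examples, and sections 1.7.1 and 1.8.1 report a drug-related ventricular tachycardia SAE in Phase I, rated mild.

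The summary of changes shows that score 2 patients were admitted, and the SAE-based rule introduced, in the current version. It lists edits to 8.1.6 and 8.2 but none to 8.1.2. That may explain the mismatch, though it proves nothing by itself.

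**Working it through.** The plan states no figure on this point, so there is none to reproduce. The check sets the provisions side by side.

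**1. Which events count, on the natural reading of 8.1.2**

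| Event | SAE? | In the 10.5 list and rule? |
|---|---|---|
| Death, any location | Yes | Yes |
| Additional organ failure, any location | Yes | Yes |
| Life-threatening, survived, no added organ failure; ward patient moved to ICU | Yes | Yes |
| The same event; patient already in ICU | No | No |
| The same event; ward patient treated without transfer | No | No |

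The last two rows are the gap. Neither depends on how grave the event is.

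**2. Other life-threatening criteria in the protocol**

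- 8.1.3 defines Grade 4 as life-threatening, with no ICU condition.
- The sponsor's FDA duty in 8.3 covers life-threatening suspected reactions that are unexpected, with no ICU condition.
- Sites must report immediately only what 8.1.2 calls serious, and the sponsor's clock starts on receipt. A reaction that falls within the sponsor's duty can therefore arrive by the slower route.

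**3. Illustration only; every rate below is assumed**

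Per-arm numbers at the two reviews are 135 × 0.50 = 67.5, taken as 67, and 135 × 0.75 = 101.25, taken as 101. Assume:

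- a ventilated share s of 10% to 30%;
- survived life-threatening events without organ failure in 10% (placebo) and 30% (CD24Fc) of ventilated patients;
- life-threatening events leading to ICU admission in 5% and 15% of the other patients;
- all other SAEs in 15% of both arms, without overlap.

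Events left off the list = n × s × rate:

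- 50% review: placebo 67 × 0.10 × 0.10 = 0.7 to 67 × 0.30 × 0.10 = 2.0; CD24Fc 67 × 0.10 × 0.30 = 2.0 to 67 × 0.30 × 0.30 = 6.0.
- 75% review: placebo 1.0 to 3.0; CD24Fc 3.0 to 9.1.

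SAE proportion on the natural reading = 0.15 + (1 − s) × 0.05 for placebo and 0.15 + (1 − s) × 0.15 for CD24Fc. Counting all events adds s × 0.10 and s × 0.30. At s = 0.10 this gives 0.195 v 0.285 on the natural reading and 0.205 v 0.315 with all events. At s = 0.30 it gives 0.185 v 0.255 and 0.215 v 0.345.

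Power uses the normal approximation at two-sided 0.05. That level is also assumed, since the rule names none. Power = Φ{[|pT − pC| − 1.96√(2p̄(1 − p̄)/n)] / √([pC(1 − pC) + pT(1 − pT)]/n)}.

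| Review | s | All events counted | Natural reading |
|---|---|---|---|
| 50% (n = 67) | 10% | 0.30 | 0.23 |
| 50% (n = 67) | 30% | 0.39 | 0.16 |
| 75% (n = 101) | 10% | 0.43 | 0.32 |
| 75% (n = 101) | 30% | 0.54 | 0.22 |

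What follows from the text is that these events are not counted. The loss of power follows only if the drug raises their rate, and its size depends wholly on the assumptions.

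**The case against.** The strongest reply is that the sentence need not mean this. The ICU phrase stands directly after the words on COVID-19 progression and could qualify them, which would leave no ICU condition on the adverse event. The verb could also mean needing ICU-level care. This stands as a point about ambiguity, but it does not remove the problem: sites that read the clause differently will classify the same event differently.

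Second, the investigator or the sponsor may judge seriousness. That gives room to decide whether a listed outcome has occurred. It does not add an outcome to the list.

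Third, the events are not invisible. Grade III to V events are recorded, assessed for causality and sent to the sponsor. Section 11.5 also sends CRO safety reports to the DSMB and has the Medical Monitor and sponsor review them monthly. The synopsis allows extra DSMB meetings, and under 8.3 the Medical Monitor may stop the study for safety. A reader might infer that SAEs are the DSMB's only safety information; the documents do not support that. But the content of the CRO reports is not specified, and no section makes non-serious events part of the stopping rule. The Grade III to V backstop also has a flaw: in several places 8.1.6 and 8.2 say Grade III or V, which literally skips Grade IV. This is probably a slip.

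Fourth, randomization balances baseline score in expectation. The baseline gap therefore mainly costs sensitivity and does not by itself bias the comparison. That stands.

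**Conclusion.** The point holds in a limited form. On the natural reading of 8.1.2, a life-threatening event survived without additional organ failure by a patient already in ICU is not an SAE. It is left off the list in 10.5, out of the stopping rule and outside immediate site reporting. This rests on reading the ICU phrase as a condition on the adverse event, and on score 2 patients being in ICU, as 11.1.3 describes.

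Two stronger readings are tempting and should be resisted:

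- A reader might infer that the stopping rule misses life-threatening events in the sickest patients generally. It does not: death and additional organ failure count wherever they occur.
- A reader might size the problem by assuming that 10% to 20% enter at score 2, giving 270 × 0.10 = 27 to 270 × 0.20 = 54 patients. That counts patients exposed to the gap, not events missed, and the documents give no such share.

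The number of missed events, and whether a stopping decision would change, cannot be stated from the documents. The correction is still worth making, because a safety trigger should not depend on where the patient lies at onset.

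**What to change.** Remove the ICU condition from the life-threatening limb of 8.1.2. Possible wording: *a life-threatening adverse event, regardless of ICU admission or location, other than progression of COVID-19*. This settles the ambiguity, matches the life-threatening criterion in 8.3, and brings these events into the SAE list and stopping rule in 10.5 and the synopsis.

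Adding only patients already in ICU would not be enough. A life-threatening event treated on the ward without transfer would still not be an SAE, while the sponsor's duty in 8.3 has no ICU condition.

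The cost is one clause, a notice to sites and a few more SAE reports. For patients already enrolled, recorded Grade IV events can be reclassified under the new wording before the next DSMB review.

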8.1.3. Criteria for Determining the Severity of Adverse Events

AEs not listed in the CTCAE 5.0 version table can be classified into grades 1-5 with reference to the following table.

Grade	CTCAE
1	Asymptomatic or mild; only clinical or diagnostic observations; no intervention required
2	Moderate: Small, local, or non-invasive measures are required; age-related instrumental daily life activities (ADL) are limited *.
3	Serious or medically significant but not immediately life-threatening: hospitalization or lengthening of hospital stay required; disability, limited autonomic ADL **.
4	Life-threatening: urgent measures are needed. Intervention indicated to prevent permanent impairment, persistent disability or death.
5	deaths related to adverse events

8.1.4. Relationship to Study Drug

All Grade III-V adverse events (AEs) must have their relationship to study intervention assessed by the clinician who examines and evaluates the participant based on temporal relationship and his/her clinical judgment. The degree of certainty about causality will be graded using the categories below.

- **Related** – There is evidence to suggest a causal relationship, and the influence of other factors is unlikely. The clinical event, including an abnormal laboratory test result, occurs in a plausible time relationship to study intervention administration and

cannot be explained by concurrent disease or other drugs or chemicals. The event must be pharmacologically or phenomenologically definitive.

- **Unlikely to be related** – A clinical event, including an abnormal laboratory test result, whose temporal relationship to study intervention administration makes a causal relationship improbable (e.g., the event did not occur within a reasonable time after administration of the study intervention) and in which other drugs or chemicals or underlying disease provides plausible explanations (e.g., the participant’s clinical condition, other concomitant treatments).
- **Not Related** – The AE is completely independent of study intervention administration, and/or evidence exists that the event is definitely related to another etiology. There must be an alternative, definitive etiology documented by the clinician.

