1.7. Clinical Experience of CD24Fc in Humans

1.7.1. Phase I Summary:

OncoImmune Inc. has developed and manufactured clinical grade CD24Fc for use in humans. CD24Fc has been tested in a Phase I clinical trial in healthy human subjects, and this study showed preliminary safety of single dose CD24Fc by IV administration. A total of 40 subjects were randomized in 5 cohorts of 8 subjects, and 39 subjects completed the study. CD24Fc was administered via IV infusion over 1 hour at doses ranging from 10 to 240 mg, and the subjects were followed over a six-week period. A MTD was not encountered.

In general, adverse events were mild to moderate in severity. The most common AEs were headache (6 [15.0%] subjects), accidental burns second degree (3 [7.5%] subjects), non-sustained ventricular tachycardia (2 [5.0%] subjects), and upper respiratory tract infection (2 [5.0%] subjects). The rates of the AEs were similar in the placebo control group. The SAE of ventricular tachycardia was considered mild in severity by the investigator and did not lead to discontinuation of the subject from the study. This SAE was considered to be drug related due to its close temporal proximity to dosing, though similar short, isolated episodes of non-sustained ventricular tachycardia may be seen in up to 4% of normal, healthy populations. No deaths or adverse events leading to discontinuation occurred during the study.

1.7.2. Phase IIa Summary:

A Phase IIa prospective randomized double-blind clinical trial of CD24Fc for acute GVHD prophylaxis in myeloablative matched unrelated donor HCT was initiated in July 2016. The first patient was enrolled in Sept 2016. A total of 24 patients were enrolled in three cohorts, 240mg single dose given at day -1, 480mg single dose at day -1, 480-240-240mg multi-dose given on day -1, day 14 and day 28, with 6 patients receiving CD24Fc and 2 patients receiving placebo in each cohort. The last patient was enrolled in Dec 2017. The last patient reached one year post-HCT in December 2018. Data was locked and the final clinical study report (CSR) was submitted to FDA in April 2019. In total there are 18 patients in the CD24Fc group and 6 patients in the placebo group (3:1 randomization). All planned dosages were delivered on schedule.

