10.4.4. Safety Analysis

Adverse events will be summarized according to the system organ classification (SOC) and preferred term (PT) coded by the MedDra thesaurus. The number of AE, TEAE, SAE, and ADR cases, incidence and number of cases were summarized in each arm.

The results of specific laboratory tests, electrocardiograms, vital signs, and physical examinations will be summarized and their relative baseline changes will be reviewed. Where applicable, the baseline value and the value at each time point after the baseline are presented in the form of a crosstab.

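### The three causality categories in Section 8.1.4 leave out the plausibly timed event that COVID-19 or co-medication might also explain, and they are not reconciled with the SAE standard in Section 8.3

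*Combined protocol and SAP*

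**What the plan says.** Section 8.1.4 requires a causality assessment for every Grade III to V adverse event, based on timing and the examining clinician's judgment: "The degree of certainty about causality will be graded using the categories below". There are three categories.

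- *Related*: "There is evidence to suggest a causal relationship, and the influence of other factors is unlikely". The timing must be plausible, and the event must be one that "cannot be explained by concurrent disease or other drugs or chemicals. The event must be pharmacologically or phenomenologically definitive".
- *Unlikely to be related*: an event "whose temporal relationship to study intervention administration makes a causal relationship improbable" "and in which other drugs or chemicals or underlying disease provides plausible explanations". The two conditions are joined, so both must hold.
- *Not Related*: the event is wholly independent of the study drug and/or definitely due to something else, and the clinician must document a definitive alternative cause.

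Section 8.3 uses a different test for SAEs. The report must contain "an assessment of whether there is a reasonable possibility that the study intervention caused the event".

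Section 10.4.4 then plans the tabulation: "The number of AE, TEAE, SAE, and ADR cases, incidence and number of cases were summarized in each arm". ADR is not defined there or elsewhere in the protocol.

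**The concern.** A causality scale should give every event a place. This one appears to have none for the event that is hardest to judge in acutely ill patients: it follows the infusion at a plausible interval, and the underlying disease or another drug could also have caused it. All participants are hospitalised and need oxygen support or ventilation (Section 4.1). Best available treatment may include immune modulators and experimental antivirals (Section 6.4), and the synopsis adds convalescent plasma. Competing explanations are therefore to be expected.

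Safety is part of the primary objective (Section 2.1), and a relatedness-based count is among the planned summaries. If investigators have no valid option for ambiguous events, they will choose one by habit. The relatedness data will then depend on the site as well as on the event. For an SAE, two different standards apply to the same event, with no statement of how they correspond.

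**Working it through.** The plan states no figure on this point, so there is nothing to reproduce. The check applies the three definitions literally to each combination of timing (plausible or improbable) and alternative explanation (none, possible but unproven, definitive). That gives 2 × 3 = 6 cells.

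| Timing | Alternative cause | Category under Section 8.1.4 |
|---|---|---|
| Plausible | None | *Related*, provided the event is also definitive |
| Plausible | Possible, unproven | None |
| Plausible | Definitive | *Not Related* |
| Improbable | None | None |
| Improbable | Possible, unproven | *Unlikely to be related* |
| Improbable | Definitive | *Unlikely to be related* or *Not Related* |

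Two of the six cells have no category. The second row is the one that matters here. It fails *Related* because another explanation exists, fails *Unlikely to be related* because the timing is plausible, and fails *Not Related* because no definitive cause is documented. No other section supplies a category or says what to do with an event that fits none.

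**Is this cell foreseeable?** Competing causes follow from Sections 4.1 and 6.4. On timing, Section 1.9.2 gives a mean half-life of 406.648 h for the 480 mg single dose, and 406.648 / 24 = 16.9 days. Follow-up is 28 × 24 = 672 h, or 672 / 406.648 = 1.65 half-lives. Section 1.13 claims more than 50% pharmacological activity after 14 days (Table 4, average 52.4%). Adverse events are collected from Day 1 to Day 29 (Section 8.1.6). With drug present for much of that window, improbable timing will often be hard to argue. The documents give no frequency for such events.

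**Does Section 8.3 close the gap?** Only for SAEs. Section 8.1.2 limits these to death, life-threatening events other than COVID-19 progression that require ICU admission, and organ failure beyond COVID-19 respiratory failure. A Grade III or IV event outside that definition is judged by Section 8.1.4 alone. An SAE is judged by both sections, one asking for a definitive event and the other for a reasonable possibility.

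**Possible effect on ADR counts (illustration only).** Assume that ADR means *Related* under Section 8.1.4 and that definitions are applied literally. Let q be the share of true drug reactions that also have a plausible COVID-19 or co-medication explanation. The share counted is then at most 1 − q:

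- q = 0.3: 1 − 0.3 = 70%
- q = 0.5: 1 − 0.5 = 50%
- q = 0.9: 1 − 0.9 = 10%

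The documents give neither q nor the ADR definition, so this range shows the mechanism and is not an estimate.

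**The case against.** The strongest reply is that little depends on this scale. Grade III to V events are recorded whatever their relationship to treatment (Section 8.1.6), and treatment-emergent events are defined without a causality filter (Section 8.2). AEs, TEAEs and SAEs are all summarised by arm (Section 10.4.4). SAEs go to the sponsor whether or not they are thought related, and the reporting provisions of Section 8.3 use their own wording, not the Section 8.1.4 categories. The stopping rule in Section 10.5 concerns SAEs as such. All of this stands. The randomised, blinded comparison of all events is intact, and that limits the seriousness of the gap.

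The reply also answers two stronger readings.

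A reader might infer that ADR counts must approach zero by construction. That does not follow. The ambiguous event is shut out of all three categories, so the text does not push it in one direction. Section 8.1.4 also allows clinical judgment, and ADR is never tied to *Related*. Inconsistent coding is the safer prediction.

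A reader might also infer that the two notable drug-related events in Section 1.7 could not have been called related under this scale. The documents do not show that. Of the Phase I ventricular tachycardia, Section 1.7.1 says: "This SAE was considered to be drug related due to its close temporal proximity to dosing". It occurred in a healthy volunteer, and a background rate of up to 4% in healthy people is neither concurrent disease nor another drug; only the requirement of a definitive event is arguable. Section 1.7.2.2 calls the hyperglycemia at 480 mg possibly drug related, but Section 1.8.2 records it as study drug-related and Section 1.11 as the only drug-related SAE. The causality scales used in those trials are not in the documents.

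None of this supplies the missing category. A protocol that asks for a relatedness grade on every Grade III to V event should offer one that fits.

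**Conclusion.** Wrong as written, minor. Read literally, the three categories are not exhaustive, and the cell they omit is foreseeable in this population. *Related* also sets a higher bar than the Section 8.3 test for SAEs, with no mapping between them. The expected result is inconsistent relatedness coding, chiefly for non-serious Grade III and IV events. An ADR under-count is possible only if ADR is derived from *Related* and ambiguous events are coded elsewhere; its size cannot be computed from the documents. That such events will be frequent is inferred from the eligibility criteria, the permitted co-medication and the half-life, and is not a documented figure. Event capture, the all-event comparisons by arm, SAE reporting to the sponsor and the DSMB stopping rule are unaffected.

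**What to change.** 1. Add to Section 8.1.4 a category *Possibly related*: timing is plausible, and another cause is also possible but not established.
2. State that *Related* or *Possibly related* corresponds to a reasonable possibility in Section 8.3, so that AEs and SAEs are judged by one rule.
3. Define ADR in Section 10.4.4 as *Related* or *Possibly related*, and tabulate it by category and arm.

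The cost is some protocol wording and one more option on the eCRF. Randomisation, sample size and the primary analysis do not change. The downside is that more events in both arms will be labelled related, and with a half-life of about 17 days the label will be less specific. The comparison of all events by arm should therefore remain the main safety comparison, with the ADR table as a supplement.
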